While these promising results may well address the critical limitations of other peanut OIT methods, an important point to emphasise is that desensitisation actually accounts for only the first year of treatment, after which regular maintenance of peanut ingestion demands much longer patience and perseverance. This is of great importance because many children dislike the taste of peanut and can be distressed by the association between taste and past allergic experience. Furthermore, having developed a lifestyle of avoidance, this may actually be considered preferable to daily ingestion of peanuts. It is therefore timely to shift focus from initial safety to ongoing adherence.

Poor treatment adherence in ongoing maintenance therapy

The proportion of peanut-desensitised children dropping out from regular ingestion is not clear, but known to be high. In a recent long-term follow-up study of peanut sublingual immunotherapy involving 40 subjects aged 12-40 [13], 37 achieved desensitisation but 23 (62%) had chosen to discontinue treatment within 3 years. In the follow-up study of

PPOIT by Hsiao et al. (published on line, Lancet Child Adolescent Health, 2017 1:97-105), of the 24 children reviewed 4 years after initial desensitisation (original n=31), 8/24 (33%) had discontinued eating peanuts by choice while the fate of the other 7 (n=31-24) was unknown. In our own experience with the pilot study, 11 treated patients were contacted by telephone approximately one year after completion (one of the original 12 could not be contacted), and only 5 of them (45%) were still eating peanuts regularly, despite being told to continue eating after desensitisation. This indicates a drop-out rate in excess of 50% over time, which needs to be improved.

Limitations of current literature

A major design-limitation of all currently published OIT studies is that they do not incorporate a well-structured protocol for maintenance therapy post-desensitisation. This may contribute to non-adherence. A well-designed and high-quality post-desensitisation study is therefore urgently needed to make best use of the time and expense already put into OIT while maintaining long-term benefit of desensitisation in the years that follow.

Psychological considerations and quality of life

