The questionnaires will be printed in hard copies and administered to parents at Baseline, 6-months and 12-months respectively at Allergy SA, at the same interview when skin tests are also performed and blood samples taken. Some questionnaires will be completed at the site but the remaining unanswered questions will be allowed to take home and be answered at a more leisurely pace. Parents will be given a pre-addressed and reply-paid envelope to send the answers back to the RA, who will check with parents if she has not received the envelope after 2 weeks.

The following are the lists of questionnaires:

Children:

- Quality of life Peanut allergy PedQL (Pediatr Allergy Immunol 2003;14:378);
- **Depression and anxiety scores -** Revised Children's Anxiety and Depression Scale (RCADS), (https://www.corc.uk.net/outcome-experience-measures/revised-childrens-anxiety-and-depression-scale-and-subscales/)
- Stress Perceived Stress Scale for children (PSSC), (https://www.researchgate.net/publication/277630701_The_Perceived_Stress_Scale _for_Children_A_Pilot_Study_in_a_Sample_of_153_Children).

Parents:

- Quality of life
 - o Food Quality of Life Questionnaire Parent Form (DunnGalvin et al 2008)
 - o Food Allergy Quality of Life Parental Burden Scale (Cohen et al 2004)
- **Depression and anxiety scores** Depression, Anxiety, and Stress Scale (DASS) (Lovibond & Lovibond, 1995).
- Stress perceived stress scale (PSS).

Sample Size and Statistical Analysis:

- Analysis will be undertaken according to intention-to-treat principle.
- Dichotomous outcomes, including successful completion of oral food challenges, proportion experiencing adverse effects, and adequate treatment adherence, will be assessed by calculating a risk ratio (RR) with 95% CI, determined with a log-binomial model.
- Food related QOL at end of trial will be compared between groups using linear-mixed models, adjusting for food related QOL.
- Appropriate statistical analyses for immunological parameters will be undertaken according to underlying distribution of each variable (i.e. IgE, IgG4, skin pricks). Differences between groups at baseline, 6 months and 12 months will be compared using *Two Sample t-Test* or *Wilcoxon Rank Sum Test* for parametric and non-parametric data respectively. Differences within group across time will be compared

using *Paired t-Test* or *Wilcoxon Signed Ranks Test* for parametric and non-parametric data respectively.

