• A p-value of less than 0.05 will be considered to indicate statistical significance.

Power calculation:

The overall sample size is capped according to the number of children who have complete the original HYPES study. HYPES enrolled 69 children and we estimate that 60 of these would consist to this post-HYPES study. While the sample is small, this study will provide critical data to inform the development of larger clinical trials and demonstrate the feasibility of evaluating outcomes associated with ongoing maintenance regimens following successful peanut desensitisation. Based on the limited number of eligible children, a total of 60 participants (30 in each group) would provide 80% power (alpha 0.05) to detect an absolute difference of 25% with respect to successful completion of OFC or non-adherence/withdrawal from treatment. Previous literature and our own clinical experience indicates that non-adherence to peanuts is a major problem, with 33-62% of children becoming non-adherent within 12-36 months of successful peanut desensitisation. Therefore our study is sufficiently powered to determine whether frequency of peanut ingestion is associated with a 25% or greater difference with respect to treatment adherence.

Flow Chart

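### For adherence, 30 per arm gives about 50-70% power for a 25-point difference at the protocol's own non-adherence rates, not 80%; for OFC success the 80% is unsupported

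*Protocol*

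**What the plan says.** Under Power calculation, the protocol states that "a total of 60 participants (30 in each group) would provide 80% power (alpha 0.05) to detect an absolute difference of 25" percent. The sentence covers two endpoints: successful completion of the OFC, which is the primary outcome, and non-adherence or withdrawal from treatment. It does not give the rates assumed in each arm, the test or the sidedness.

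The paragraph then describes non-adherence as a major problem, "with 33-62% of children becoming non-adherent within 12-36 months of successful peanut desensitisation", and draws a conclusion: "Therefore our study is sufficiently powered to determine whether frequency of peanut ingestion is associated with a 25% or greater difference" in adherence. It also says that the sample is capped by the number of children who completed the preceding trial, that it is small, and that the study will inform larger trials.

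The analysis is fixed under Sample Size and Statistical Analysis. Dichotomous outcomes, with OFC completion and adequate adherence both named, "will be assessed by calculating a risk ratio (RR) with 95% CI, determined with a log-binomial model". On the significance level: "A p-value of less than 0.05 will be considered to indicate statistical significance".

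**The concern.** Power for a fixed absolute difference depends on where the two proportions lie. The variance of a proportion is largest near 50%, so 25 points is much harder to detect there than near 0% or 100%. The only rates in the power paragraph, 33-62% non-adherence, lie in the difficult region, and 30 per arm looks too few for 80% power.

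The protocol hypothesises that weekly ingestion gives better adherence than daily ingestion, and it tells the reader that the trial can settle a difference of 25 points or more. If the true power is near one half, a non-significant adherence result is far weaker evidence than that sentence suggests. Whoever plans the larger trials this study is meant to inform would also start from too small a number per arm.

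**Working it through.** **Inputs.** n = 30 per arm, alpha 0.05, difference 0.25, and non-adherence of 33-62%, all from Power calculation. The group's own pilot adds one rate (Poor treatment adherence in ongoing maintenance therapy): 5 of 11 children were still eating peanuts regularly about one year on, so 6/11 = 55% were not. Two-sided testing is assumed, because a 95% CI for the risk ratio corresponds to a two-sided 5% test and no one-sided test is mentioned.

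**Formula (normal approximation, pooled variance under the null).** With p̄ = (p1 + p2)/2,

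- SE0 = √[2·p̄(1 − p̄)/n]
- SE1 = √[(p1(1 − p1) + p2(1 − p2))/n]
- power = Φ[(|p1 − p2| − 1.96·SE0)/SE1]

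**Attempt to reproduce 80%.** Example, 62% vs 37%: p̄ = 0.495, SE0 = 0.1291, SE1 = 0.1250, so (0.25 − 0.2530)/0.1250 = −0.024 and Φ = 49.0%. Example, 33% vs 8%: p̄ = 0.205, SE0 = 0.1042, SE1 = 0.0991, so (0.25 − 0.2043)/0.0991 = 0.461 and Φ = 67.8%.

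| Non-adherence, arm 1 vs arm 2 | Power, two-sided | Power, one-sided 0.05 | n per arm for 80% (two-sided) |
|---|---|---|---|
| 33% vs 8% | 67.8% | 78.6% | 40 |
| 33% vs 58% | 49.4% | 62.2% | 62 |
| 50% vs 25% | 51.7% | 64.3% | 58 |
| 55% vs 30% (pilot rate) | 49.9% | 62.7% | 61 |
| 62% vs 37% | 49.0% | 61.8% | 62 |
| 62% vs 87% | 60.8% | 72.6% | 47 |

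The two-sided range is 49-68%, so the stated 80% is not reproduced at any of these rates.

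**Other methods, same rates, two-sided.**

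- Unpooled variance: 52-71%.
- Exact enumeration, uncorrected chi-square: about 50-70%.
- Exact enumeration, Fisher's test: about 40-58%.
- Exact enumeration, Wald test on the log risk ratio (close to the planned analysis): about 50-59%.

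**Where 80% does arise.** By the same normal approximation, 2% vs 27%, or equivalently 98% vs 73%, gives SE0 = 0.0909, SE1 = 0.0850, (0.25 − 0.1782)/0.0850 = 0.845 and Φ = 80.1%. The exact boundary depends on the test: enumeration of the uncorrected chi-square still gives 81% at 4% vs 29%, while Fisher's test gives 71% at 2% vs 27%. Under each of these tests, such rates lie well outside 33-62%.

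**Difference detectable with 80% power at 30 per arm (two-sided, normal approximation).** From 33% downward, 27.9 points; from 50%, 33.4 points; from 62% downward, 35.2 points. That is about 28 to 35 points.

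**The 12-36 month label.** Under Poor treatment adherence in ongoing maintenance therapy, the 33% is 8/24 "of the 24 children reviewed 4 years after initial desensitisation". The 62% (23/37, within 3 years) and the pilot's 55% at about one year do fit the stated window.

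**The case against.** Four points can be made for the protocol.

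*The sentence also covers the OFC, where rates may be near the ceiling.* This stands. No OFC rate is given, and the protocol hypothesises that children who continue eating peanuts stay desensitised. At 98% vs 73% the 80% is right by normal approximation. A reader might infer that the power is equally wrong for the primary outcome, since the final OFC requires full adherence in the preceding two weeks and the analysis is by intention to treat. That inference needs children who are not challenged to be counted as failures, and the protocol does not say so.

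*A one-sided test may have been meant.* One-sided 0.05 brings the most favourable case (33% vs 8%) to 79%, but 62% vs 37% only to 62%. The document mentions no one-sided test, and its planned interval is two-sided.

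*The protocol is candid about size.* It says that the sample is capped and small and that the study informs larger trials, and a confidence interval would show the imprecision. This softens the consequence. It does not correct the 80% figure or the conclusion drawn from it in the same paragraph.

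*Attrition.* A reader might infer that dropout lowers the power further. For adherence this does not follow automatically, because withdrawal from treatment is part of the endpoint and need not remove a child from the denominator. The point does not rely on it.

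**Conclusion.** The stated power is wrong for adherence and unsupported for OFC success. At the 33-62% non-adherence the protocol itself cites, 30 per arm gives about 50-70% power for a 25-point difference, and 40-58% with Fisher's test. Reaching 80% would take 40 to 62 per arm for a 25-point reduction from those rates. The result assumes two-sided 5% testing, all 30 per arm analysed, and one arm at a rate within the cited range.

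Two stronger readings go beyond the document. The first is that the OFC power has been shown to be wrong: without a base rate it can be neither confirmed nor refuted. The second is that the protocol intends a null result to rule out a 25-point effect. It says nothing of the kind; the sufficient-power sentence merely invites that reading. The mislabelled time window for the 33% is a small factual slip and does not affect the power error.

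**What to change.** Keep N at 60 and change the wording under Power calculation.

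1. Replace the 80% sentence with: *With 30 per group (two-sided alpha 0.05, normal approximation), power to detect a 25-point difference in non-adherence is about 50-70% when non-adherence in one group is 33-62%; differences of about 28-35 points are detectable with 80% power.*
2. For the OFC, state the success rates assumed in each arm and the power that follows from them, or drop the OFC power claim.
3. Delete the conclusion that the study is sufficiently powered for a difference of 25% or more in adherence.
4. Correct the 12-36 month description, since the 33% was observed at 4 years.

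The cost is wording only. Recruitment, conduct and analysis do not change, but the stated power becomes less favourable.

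### The adherence rates behind the claim of sufficient power are mislabelled, and even at face value 30 per arm gives about 49-68% power, not 80%, for a 25-point reduction

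*Protocol*

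**What the plan says.** The Power calculation caps the trial at 60 children, 30 per group. It claims 80% power at alpha 0.05 "to detect an absolute difference of 25% with respect to successful completion of OFC or non-adherence/withdrawal from treatment". No daily-arm rate is attached to that difference.

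For adherence it then gives a basis: "Previous literature and our own clinical experience indicates that non-adherence to peanuts is a major problem". The size that it puts on this problem is "33-62% of children becoming non-adherent within 12-36 months of successful peanut desensitisation". The next sentence draws the conclusion: "Therefore our study is sufficiently powered to determine whether frequency of peanut ingestion is associated with a 25% or greater difference" in adherence.

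The Background, under the heading on poor adherence in maintenance therapy, describes three sources:

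- A sublingual study: "peanut sublingual immunotherapy involving 40 subjects aged 12-40 [13], 37 achieved desensitisation but 23 (62%) had chosen to discontinue treatment within 3 years".
- A follow-up of oral immunotherapy with a probiotic: "of the 24 children reviewed 4 years after initial desensitisation (original n=31), 8/24 (33%) had discontinued eating peanuts by choice". The other 7 of the 31 were not accounted for.
- The group's own pilot in children: 5 of 11 reached by telephone at about one year were still eating peanuts regularly, so 6 of 11 were not.

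Hypothesis 4 predicts better adherence at 12 months with weekly ingestion. The planned analysis of dichotomous outcomes is a risk ratio with a 95% CI.

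**The concern.** The range is the stated premise for the word 'Therefore' in the power claim, yet neither of its ends matches its label. The low end was measured at 48 months, outside a 12-36 month window. The high end comes from a mixed-age group treated by another route, so 'children' does not describe it. Adherence in this trial is judged at 12 months in children after oral immunotherapy.

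The conclusion also has to follow from the range. Power for a fixed absolute difference depends on the base rate, so a 25-point difference cannot carry one power figure across rates from 33% to 62%. If the true power is nearer one half, the trial could easily miss a 25-point benefit of weekly ingestion. A reader who trusted the protocol would then take the null result as evidence that frequency does not matter.

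**Working it through.** **Sources against label**

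| Figure | Count | Population and route | Time point | Fits 'children, 12-36 months'? |
|---|---|---|---|---|
| 33% | 8/24 = 33.3% | children, oral with probiotic | review at 4 years | population yes, time no |
| 62% | 23/37 = 62.2% | ages 12-40, sublingual | within 3 years | time yes, population no |
| 55% | 6/11 = 54.5% | children, the group's two-step boiled-to-roasted regimen | about 1 year | yes, but n = 11 |

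The percentages are computed correctly; the description is what fails. The exact (Clopper-Pearson) 95% interval for 6/11 runs from the 2.5% point of Beta(6, 6) to the 97.5% point of Beta(7, 5), that is 23.4% to 83.3%.

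Hypothesis and Expected Outcomes has a related slip. It credits the literature with more than half of treated children stopping within 2-3 years, but the only published rate for children in the Background is the 33% at 4 years.

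**Attempt to reproduce the 80%**

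Inputs from the Power calculation: n = 30 per arm, alpha 0.05, difference 0.25. Sidedness is not stated. Two-sided is used because it matches the planned 95% CI. The reduction is from daily (p1) to weekly (p2), as in Hypothesis 4. The mean of p1 and p2 is written p̄.

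- SE0 = √(2·p̄(1 − p̄)/30)
- SE1 = √((p1(1 − p1) + p2(1 − p2))/30)
- Power = Φ((0.25 − 1.96·SE0)/SE1)

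| p1 vs p2 | SE0 | SE1 | z | Power | n per arm for 80% |
|---|---|---|---|---|---|
| 33% vs 8% | 0.1042 | 0.0991 | 0.461 | 68% | 40 |
| 54.5% vs 29.5% | 0.1274 | 0.1233 | 0.002 | 50% | 60 |
| 62% vs 37% | 0.1291 | 0.1250 | −0.024 | 49% | 62 |
| 27% vs 2% | 0.0909 | 0.0850 | 0.845 | 80% | 30 |

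The 80% is reproduced only near 27% versus 2%, below the protocol's range.

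**Sensitivity to method** (33%, 54.5% and 62% in turn)

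- Unpooled variance, two-sided: 71%, 53%, 52%.
- Fisher's exact test: about 57%, 40%, 40%.
- One-sided 0.05, pooled: 79%, 63%, 62%.
- One-sided 0.05, unpooled: 81%, 65%, 64%.
- A 25-point increase instead of a reduction, two-sided pooled: 49% from 33%, 54% from 55%, 61% from 62%.

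Only a one-sided test at the very bottom of the range comes close to 80%.

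**Reduction detectable with 30 per arm at 80% power** (same formula solved for the difference)

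- From 33%: 27.9 points, to about 5%.
- From 54.5%: 34.3 points, to about 20%.
- From 62%: 35.2 points, to about 27%.

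**The case against.** Several points on the other side stand.

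- The protocol cites its own clinical experience alongside the literature. The pilot supplies a figure for children at about one year, and 55% lies inside 33-62%. The pilot may also explain the 12 in '12-36 months'.
- Four years is when the 8 children were reviewed. The protocol does not say when they stopped, so some or all may have stopped by 36 months. The text does not show that they did.
- The number of children is capped by completers of the earlier trial, and the range is not shown as an input to the 80%. Relabelling it changes neither the sample size nor the analysis.
- Successful oral food challenge, the primary outcome, is covered by the same 25-point claim. No challenge success rate is given, and that half of the claim is not tested here.

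Two stronger readings are tempting and should not be made.

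- A reader might infer that none of the quoted rates says anything about children at 12 months. The pilot does, though its regimen had two steps where the feeder trial's has three, and n = 11 leaves it imprecise.
- A reader might scale the published figures back to 12 months under a constant hazard, giving 1 − (16/24)^(1/4) = 9.6% and 1 − (14/37)^(1/3) = 27.7%, and conclude that a 25-point reduction is impossible. Nothing in the protocol supports a constant hazard. Carried forward on the same assumption, the pilot would give 1 − (5/11)^4 = 96% at 4 years, against the 33% seen in the other cohort. The 9.6% also lies below the pilot's own interval. The power sentence is moreover worded for a difference in either direction.

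**Conclusion.** The point holds in two parts. First, the Power calculation and the Background contradict each other on what the 33% and the 62% are. Second, the stated power for adherence is wrong as written: across the protocol's own range, 30 per arm gives about 49-68% for a 25-point reduction, and about 50% at the pilot's rate.

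This rests on two-sided 0.05, a pooled-variance normal approximation, equal arms and no loss of participants. Other standard two-sided choices do not rescue the 80% anywhere in the range.

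A 25-point reduction can occur only if daily-arm non-adherence is at least 25%, and at exactly 25% it would require none at all in the weekly arm. No rate quoted in the protocol is that low as a point estimate, but the pilot's interval (23-83%) does not exclude it. This is a condition to state, not a finding that the target is unattainable. The consequence is confined to what the trial may claim about adherence.

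**What to change.** In the Power calculation:

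1. Replace the single range with the three sources as the Background gives them: 8/24 (33%) of children at a 4-year review, with 7 of 31 unknown; 23/37 (62%) of people aged 12-40 on sublingual treatment within 3 years; 6/11 (55%) of children in the pilot at about one year. Bring the matching sentence in Hypothesis and Expected Outcomes into line.
2. State the assumed 12-month non-adherence rate in the daily arm and its uncertainty. If the pilot is used, give the 23-83% interval.
3. For adherence, replace the 80% power and the claim of sufficiency with the reduction detectable at 80% power and 30 per arm, two-sided 0.05: about 28 points at 33%, 34 at 55% and 35 at 62%. Add that a 25-point reduction needs a daily-arm rate above 25%.

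The cost is wording only. Sample size, randomisation and analysis stay as they are. The justification becomes less favourable, but it fits the protocol's existing statement that the sample is small and meant to inform larger trials.
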